Our decision to make the clinic the primary unit of analysis is because of the known sociodemographic and clinical differences in patients (pre-pandemic) who chose to use telemedicine. Patients that use telemedicine for instance, tend to be younger and are more likely to be female than patients that used other sites of care.²⁸ Therefore, in our primary analysis, we will exploit the change in availability for telemedicine services at the clinic level as an independent determinant of telemedicine use, leveraging an intent-to-treat approach to evaluate the association between clinic-level telemedicine availability and patient outcomes. We will further improve the internal validity of the study by matching clinics using clinic-level characteristics. This is further described in the analytic methods below.

Outcomes

We will analyze measures of health care utilization and quality from Medicare and commercial (Anthem and Humana) claims and CRN EHR data. Our primary outcome measures include avoidable emergency department (ED) admissions, potentially preventable hospital admissions, and continuity of care.²³ Secondary measures will include evidence of

PRINCIPAL INVESTIGATOR: [name]; [name]

controlled disease (as indicated by condition-specific measures endorsed by the National Quality Forum (NQF) or HEDIS) and days at home. A list of outcome measures is included in Table 1 below. These primary and secondary outcome measures will be constructed at the patient-month level, and we will examine 30-day, 60-day, 6-month and one-year outcomes where data are available. We have operationalized the majority of these measures through a previous PCORI health system demonstration grant, in collaboration with OneFlorida.

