American Indian	23	12	0	35
Asian	41	29	0	70
Native Hawaiian or Other Pacific Islander	23	13	0	36
Black or African American	190	79	0	269
White	1547	887	0	2434
More than one race	2260	973	0	3233
Unknown or not reported	2688	1482	0	4170
Racial Categories: Total of Hispanics or Latinos	6772	3475	0	10247

*Estimates are counts of ambulatory patients seen at the 4 sites since January 1 2020; due to time constraints, this table includes some patients seen in specialty settings who will not be included in the final analysis.

An additional PCORI deliverable for this project (scheduled for 2021) is to provide a more detailed estimate of patients meeting our eligibility criteria and covered by the two commercial insurers.

Power Calculation

Across participating sites, we estimate about 205,000 patients in primary care with one or more of the five conditions (see **tables** above). For the ED visit outcome, this sample size provides 93% power to detect a 1% difference between the treatment and comparison arms in a two-tailed test with an alpha of 0.05.

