Our sample sizes still provide sufficient power should we adopt a non-inferiority framework to test whether telemedicine visits are no less effective than in-person visits. For the ED visit outcome, if we assume that the minimum sample size is 25,000 in each of the three groups, and that between 20% and 5% of patients in the in-person arm have unplanned ED visits, we will have between 80% and 99% power to determine whether the telemedicine arm is no worse than 1 percentage point (absolute) lower than the in-person comparator. (This calculation was done with a z-test to determine a difference in proportions with a one-sided 2.5% significance level.) In fact, our study will have more power if the groups have more than 25,000 patients. For the patient satisfaction outcome, with 500 in each group, there will be 90% power with one-sided level of significance of 0.025 to determine if the decrease in mean level of patient satisfaction for the telemedicine group is no more than 0.2 standard deviations compared to the control group (in-person). We believe a 0.2 standard deviation effect size is reasonable for a non-inferiority margin because it lies below the 0.25 effect size that is typically deemed meaningful for patient satisfaction and quality of life instruments.

F. AIM 2 METHODS: DATA COLLECTION, MANAGEMENT, ANALYSIS

Data Collection Methods and Data Sources

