Another complexity making it challenging to predict the directionality of the effect of the telemedicine transition is that the rapid nationwide transition appears to have led to diverse types of telemedicine programs, ranging from relatively mature programs with well-established technology and user support, to rapidly implemented programs with less well-established technology or support. This heterogeneity may influence whether telemedicine was effective in improving access to care or patient-provider communication. It is well-established that innovations that are not highly usable, well-matched to user needs, and supported with organizational support are unlikely to promote their desired outcomes.^{38,39}

In light of the complexities described above in the causal model, we propose a nondirectional overall hypothesis that telemedicine-only, telemedicine-supplemented in-person visits, and in-person only groups will have different healthcare utilization and patient satisfaction outcomes.

Primary Analysis

Our causal model will leverage variation over time and across sites in the availability of telemedicine visits to assess the impact of a change in clinic-level availability in telemedicine on patient-level outcomes. We will use a generalized version of the difference-in-differences methodology (also known as an event study design) in an intent-to-treat framework to compare patients receiving care at clinics that have switched to telemedicine-only visits at a given time with patients at comparable clinics that have not or that used a mixture of telemedicine and in person care. This event

PRINCIPAL INVESTIGATOR: [name]; [name]

study design allows for multiple treatment periods and for the relationship between treatment and outcomes to vary over time.

The causal identifying assumption in difference-in-differences models is that outcomes in each comparator arm would have followed the same trends in the absence of exposure to telemedicine, after the onset of the pandemic.⁴⁰ While we cannot directly test this assumption, we can test whether there significantly different trends in outcomes during the months prior to the onset of the pandemic. We expect that this parallel trends assumption may hold in our study, because the transition to telemedicine during the pandemic was rapidly implemented and potentially unrelated to patient outcomes and the underlying quality of the clinic.

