We will define the degree of telemedicine exposure (dose) in two ways. First, based on the comprehensive landscape survey of primary care leaders in [Aim 1](#), we will develop a composite score indicating the robustness of the telemedicine program at each clinic site under study. Among other features, this score will take into account the total number of components and delivery modes of the telemedicine program, its focus on providing coordinated care to a patient population with chronic care needs, and staff and clinical support from the organization.

Second, we will define telemedicine exposure based on the proportion of all visits at a given clinic that are delivered via telemedicine in each month. Specifically, we will classify clinics into quartiles of telemedicine exposure based on the distribution of all telemedicine provision among clinics in this treatment arm. We will then separately analyze the relationship between our outcomes of interest and the amount (dose) of telemedicine being offered at a clinic. We will cluster all primary and secondary analysis at the clinic level, as this is the level at which the exposure occurred.⁴³

Finally, in addition to the primary intent-to-treat analysis, we are proposing an additional secondary analysis. This secondary “as treated” analysis is designed to evaluate the relationship between patient-level telemedicine exposure and our outcomes of interest. In this secondary analysis, we will characterize patients’ exposure to telemedicine after the first wave of shelter-in-place measures were put into place based on the treatment that they actually received

PRINCIPAL INVESTIGATOR: [name]; [name]

rather than based on the availability of telemedicine at the primary care clinic to which they were attributed. In this analysis, we will adjust for observed clinic and patient-level characteristics as described in the response above that may impact both the availability and choice to use telemedicine, as well as patient outcomes. Additionally, we will provide estimates from a fixed effects model in which each patient serves as their own control.

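### Neither ED power statement describes the planned analysis: the 80–99% non-inferiority power treats patients as independent, and the 93% rests on a count that is not the Medicare cohort

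*Combined protocol and SAP*

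**What the plan says.** The Power Calculation section (E. Aim 2 Methods) makes two claims about the ED outcome.

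- **Superiority.** On about 205,000 patients, described as having at least one of the five conditions: "For the ED visit outcome, this sample size provides 93% power to detect a 1% difference between the treatment and comparison arms", two-sided at 0.05.
- **Non-inferiority.** "Our sample sizes still provide sufficient power should we adopt a non-inferiority framework". The inputs are "if we assume that the minimum sample size is 25,000 in each of the three groups", "between 20% and 5% of patients in the in-person arm have unplanned ED visits" and an absolute margin of 1 percentage point, for a stated power of 80% to 99%. On method: "This calculation was done with a z-test to determine a difference in proportions with a one-sided 2.5% significance level".

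The analysis is set out elsewhere. Interventions and Comparators refers to "Our decision to make the clinic the primary unit of analysis". The Primary Analysis section (F. Aim 2 Methods) says "We will use a generalized version of the difference-in-differences methodology (also known as an event study design) in an intent-to-treat framework", adds propensity matching of clinics with a warning that clinics and sample size may be lost, and states: "We will cluster all primary and secondary analysis at the clinic level, as this is the level at which the exposure occurred".

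The cohort is also set out elsewhere. Eligibility Criteria requires two or more outpatient visits in a pre-pandemic year and, for claims analyses, continuous enrolment. Data Collection Methods and Data Sources makes Medicare fee-for-service claims the primary analysis. Table 1 lists avoidable ED admissions as the primary ED outcome.

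**The concern.** A power figure is useful only if it refers to the analysis, cohort and outcome that will be reported. Here all three differ.

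- **Analysis.** The non-inferiority figure comes from a patient-level test of two proportions. Exposure is set by clinic and inference is clustered by clinic. No clinic-level variance and no Aim 2 clinic count is given.
- **Cohort.** The footnote to Table 2 shows that the 205,000 are ambulatory patients seen at the four sites since 1 January 2020, some of them specialty patients who will be dropped. The visit criterion, continuous enrolment and Medicare fee-for-service restriction have not been applied. The refined count promised under Sample Size names only the two commercial insurers, who supply a secondary analysis.
- **Outcome.** Both statements concern ED visits or unplanned ED visits. No base rate is given for avoidable ED admissions.

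A reader therefore cannot tell what ED difference the Medicare analysis can detect, and so cannot judge a null or non-inferior result. The plan also uses the 80–99% to assure readers that a non-inferiority reading is available.

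**Working it through.** **1. Reproduce the 80–99%.** Inputs from the Power Calculation section: n = 25,000 per arm, margin 0.01, one-sided 0.025, rate p from 0.20 to 0.05. True difference taken as 0. DE is the net design effect.

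Power = Φ(0.01 / √(2p(1−p)·DE/n) − 1.96)

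At p = 0.20 and DE = 1: √(2 × 0.20 × 0.80 / 25,000) = 0.003578; 0.01 / 0.003578 = 2.795; Φ(2.795 − 1.960) = 0.798.

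| ED rate | Power at DE 1 | Largest DE that keeps 80% |
|---|---|---|
| 20% | 79.8% | 0.995 |
| 15% | 87.9% | 1.25 |
| 10% | 96.1% | 1.77 |
| 5% | 99.9% | 3.35 |

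The two ends match the stated range, so it contains no clustering allowance. The last column is (0.01/2.8016)² × 25,000 / (2p(1−p)). At a 20% rate, 80% power already needs 25,117 per arm with independent patients.

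**2. Effect of the design effect at a 20% rate.** DE 1.27 gives 70%; DE 2.03 gives 50%.

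**3. Which way does difference-in-differences push?** It can go either way. Differencing removes stable between-clinic variance. Clinic-by-time variance, unequal clinic sizes and matching losses add to the net DE. As an illustration only, with equal pre and post periods and relative to the z-test above:

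net DE = 2[(1−ICC)(1−r) + m·ICC·(1−c)]

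Here r is the patient and c the clinic pre–post correlation. Assumed values: ICC 0.005 and 83 clinics per arm (250/3, where 250 is the Aim 1A survey target, not an Aim 2 count), so m = 25,000/83 = 301.

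| c | r | Net DE | Power, 20% rate | Power, 5% rate |
|---|---|---|---|---|
| 1 | 0.7 | 0.60 | 95% | >99.9% |
| 0.9 | 0.7 | 0.90 | 84% | >99.9% |
| 0.9 | 0.5 | 1.30 | 69% | 99.5% |
| 0.8 | 0.3 | 2.00 | 51% | 95% |

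**4. Try to reproduce the 93%.** Two-proportion z-test, two-sided 0.05, N = 205,000. Several incompatible readings come close:

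- 1% relative from a 69.9% rate (the pre-period rate in the cited veterans' study), two equal independent arms: 93.0%.
- 1 percentage point from 20%, 10/90 split, independent patients: 92.5%.
- 1 percentage point from 20%, three equal arms, ICC 0.001, 820 patients per clinic (205,000/250), so DE = 1 + 819 × 0.001 = 1.82: 93.3%.

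Because the third reading includes clustering, it is not established that the 93% omits it. The scale alone decides the answer: with three equal independent arms and a 20% rate, power is 15% if the 1% is relative and 99.7% if it is 1 percentage point.

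**5. The larger effect the plan considers feasible.** For the 11% relative reduction in the veterans' study, with 25,000 per arm, power exceeds 99.9% at a 69.9% rate even at DE 7.24, and is 88% at a 20% rate and DE 4. At a 5% rate it is 83% at DE 1 and 53% at DE 2.03.

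**The case against.** The strongest reply is that nothing has been miscalculated. The 80–99% reproduces, and its test, alpha, margin, rates and group size are all stated. That is right: the fault is that the calculation is for a different analysis, not that the sum is wrong.

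Second, power may not be lost at all. The illustration uses equal pre and post periods, whereas the data run from 2017 with up to 11 months after April 2020. If three pre-periods of post-period length are pooled with exchangeable correlation (an assumption), the factor 2 becomes 4/3. The four scenarios then have DE 0.40, 0.60, 0.86 and 1.33, with power 99%, 95%, 85% and 68% at a 20% rate. This stands: neither direction nor size is established. It also shows that the stated figure is not the relevant one.

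Third, 25,000 is called a minimum, and the plan notes that larger groups give more power. At a 20% rate, 40,000 per arm would tolerate DE 1.59 and 50,000 would tolerate 1.99. The assumed 75,000 total is 36% of the 205,867 in Table 2, so a smaller cohort is already allowed for. That softens the point at 20%, but no Medicare count shows that even 25,000 per arm will be reached.

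Fourth, Table 2 is openly provisional, and the sentence promising a refined count could be read as covering all eligible patients as well as the commercial enrollees. Even so, this version gives no Medicare figure, and the 93% is stated without qualification.

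Finally, this is a retrospective cohort in existing claims, non-inferiority is a contingency beside a nondirectional hypothesis, and the clustered standard errors do not depend on the power text. All of that stands and limits the severity.

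**Conclusion.** The concern holds. The 80–99% is the power of a test on independent patients, not of the clinic-clustered difference-in-differences analysis on matched clinics. The 93% is tied to a patient count that is not the primary-analysis cohort, and its basis cannot be determined. Neither refers to avoidable ED admissions.

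The size of the error is unknown, because the clinic-level variance, Aim 2 clinic count and Medicare cohort size are not given. What follows from the plan's own figures is that, at a 20% rate and 25,000 per arm, any net design effect above 0.995 takes power below 80%, while at a 5% rate up to 3.35 is tolerable. The claim of sufficient power is therefore unsupported at the upper end of the plan's own range of rates, and more robust at the lower end. The design-effect scenarios rest on assumed ICC, clinic numbers and correlations.

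This is a reporting and planning defect that should be corrected. It does not invalidate the effect estimates or their standard errors.

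**What to change.** Replace both figures with power, or preferably minimum detectable differences, for the planned clinic-clustered difference-in-differences analysis. State:

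- the expected number of eligible, continuously enrolled Medicare fee-for-service patients, and of clinics, per arm after matching;
- the base rate of avoidable ED admissions and the clinic-by-period variance, estimated from 2017–2019 claims and shown over a range;
- the result for each pairwise contrast of the three arms;
- whether each difference is absolute or relative.

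If the non-inferiority option is kept, give its power on the same basis. The cost is a small recalculation from pre-period claims already being obtained, plus rewording, with no extra patients or data. The stated power may become less favourable.

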For the patient satisfaction outcome, with our planned survey sample size of patients with patient-reported outcomes ($n = 1,000$), we have 93% power to detect a 5% difference in patient satisfaction between the treatment and comparison arms in a two-tailed test with an alpha of 0.05. Based on an RCT examining the impact of an intensive outpatient care program on patient-reported satisfaction among a cohort of high-need patients, we need sample size of 206 patients to provide 80% power to detect a 0.26 difference in patient satisfaction (effect size determined by the study) using a 2-tailed hypothesis at an α level of .05.³⁴ Our sample size of 1,000 patients will provide greater than 80% power to detect this difference. The 0.26 difference in patient satisfaction was derived from a recent research study evaluating the impact of a medical home program on patient-reported satisfaction.⁸ The measure of patient satisfaction was based on a

PRINCIPAL INVESTIGATOR: [name]; [name]

5-point scale measuring patients' general satisfaction with care, the accessibility/convenience of care, and perceived quality of communication with their provider. Among patients who participated in both baseline and follow-up surveys, there was a statistically significant increase in mean self-reported satisfaction with the augmented medical home program compared to the standard primary care program by 0.26 points (2.90 to 3.16; $P = .04$). Although this program did not utilize any telemedicine components, we consider it reasonable to expect comparable changes in patient satisfaction among programs that have a virtual care management component that promotes frequent contact between patients and providers and allows patients to receive care in their own homes. Of note, a recent review article reports that in nearly all studies, both patients and clinicians reported high satisfaction with telemedicine visits, and either no difference between virtual and office visits in terms of the overall quality of the visit, or higher satisfaction with telemedicine visits compared to in-person only care.³⁵ Additionally, very recent work on the first 4 weeks of response to the COVID-19 crisis, which assessed patient satisfaction of telemedicine visits using a 5-point scale, found that 67% of patients who had a video or phone visit reported that the visits were "good/better" than regular in-person visits, and 96% reported that they were "somewhat/very satisfied with medical care" they received.³⁶

Our sample sizes still provide sufficient power should we adopt a non-inferiority framework to test whether telemedicine visits are no less effective than in-person visits. For the ED visit outcome, if we assume that the minimum sample size is 25,000 in each of the three groups, and that between 20% and 5% of patients in the in-person arm have unplanned ED visits, we will have between 80% and 99% power to determine whether the telemedicine arm is no worse than 1 percentage point (absolute) lower than the in-person comparator. (This calculation was done with a z-test to determine a difference in proportions with a one-sided 2.5% significance level.) In fact, our study will have more power if the groups have more than 25,000 patients. For the patient satisfaction outcome, with 500 in each group, there will be 90% power with one-sided level of significance of 0.025 to determine if the decrease in mean level of patient satisfaction for the telemedicine group is no more than 0.2 standard deviations compared to the control group (in-person). We believe a 0.2 standard deviation effect size is reasonable for a non-inferiority margin because it lies below the 0.25 effect size that is typically deemed meaningful for patient satisfaction and quality of life instruments.

F. AIM 2 METHODS: DATA COLLECTION, MANAGEMENT, ANALYSIS

Data Collection Methods and Data Sources

Our primary analysis will be the Medicare claims data analysis. We anticipate this will be the most robust analysis because of the large sample size (relative to the commercial claims data) and ability to comprehensively track patients across care settings (relative to the CRN EHR data). We will obtain 100% of 2017 through Q1 2021 Medicare fee-for-service claims data for the three states in which CRN-participating research sites are located (FL, NC, and NY). Therefore, we will be able to follow patients regardless of where they seek care, which will improve patient attribution, as well as capture the entirety of a patient's follow-up care for the utilization, continuity of care, and quality of care measures. The Medicare data will be accessed via the Centers for Medicare and Medicaid Services Virtual Research Data Center (VRDC), because (in contrast to physical copies of the data), the VRDC allows for data to be used for analysis with little lag (approximately three months following claims run-out). Use of the VRDC will enable the research team to include up to 11 months of data following the initial apex of the pandemic in April 2020. The patient attribution process will be separately conducted for each enrollee population.

Unfortunately, it will not be feasible to use federal (T-MSIS) Medicaid claims data for this project. The T-MSIS data are currently running at a 2-year lag, meaning we would not be able to obtain the data for much of the period of interest until after the grant had concluded.

In the secondary analysis, we will replicate the Medicare analysis using commercial claims data for commercially insured populations. Commercial claims data will be analyzed for Anthem and Humana commercial enrollees at the NY, FL, and NC sites for 2017 through Q1 2021, using the same analytic approach.

An additional secondary analysis will examine measures of disease control (see Table 1), utilization, and continuity of care drawn from the CRN data. Measures of disease control require EHR data that in general are not available from the commercial claims providers. In addition, the CRN data are all-payer. However, the main limitation is that if patients seek care outside of the CRN, we will not capture their utilization within CRN data. Therefore it would not be appropriate to seek to extract the ED or hospital admission data from this source.

**After submission of this grant, the three participating CRNs agreed to begin collecting data that would allow us to distinguish between telemedicine and in person visits, an item that was not available when this study was designed. This may enable us to conduct a separate analysis of telemedicine versus non-telemedicine visits at the visit level.*

Finally, we will collect PROs using REDCap surveys through the WCM REDCap database. REDCap is a secure website for building and managing online surveys and databases. It is available at each site and harmonized across institutions to facilitate data storage and management. REDCap will generate automated emails or text messages to patients containing hyperlinks to access surveys. The REDCap team will be responsible for maintenance during the study period. Table 4 summarizes the primary data sources and data elements.

Table 4

Data Sources	Data Elements
Medicare, Commercial claims, CRN structured EHR data	Diagnosis codes
Medicare, Commercial claims, CRN structured EHR data	Procedure codes
Medicare, Commercial claims, CRN structured EHR data	Demographic characteristics
Medicare, Commercial claims, CRN structured EHR data	Health care utilization
Commercial claims, CRN structured EHR data	Laboratory testing results
Medicare, Commercial claims, CRN structured EHR data	Medications
REDCap surveys	Patient experience and satisfaction

Missing data: We will assess the data source adequacy and patterns of missing data in compliance with PCORI Methodology Standards for preventing and handling missing data. More specifically, we will report the reasons for which missing data occur, which may include but are *not* limited to incomplete data on demographic characteristics in both the clinical and claims data, incomplete utilization and clinical data in the CRN data, and nonresponse to the REDCap surveys. We will also report the percentage of missing data in each of our data sources. We believe that there will be limited missing data among Medicare beneficiaries due to the completeness of Medicare FFS claims. Among commercial claims, there is also unlikely to be missing data among patients. Due to the low probability of missing data, we will use listwise deletion to deal with missing data among these data sources. Among the clinical data and PRO data sources, we will use validated statistical methods to address missing data, including multiple imputation and likelihood-based methods. Among all data sources, we will conduct sensitivity analyses to evaluate changes in the study sample and outcomes with and without missing data.

PRINCIPAL INVESTIGATOR: [name]; [name]

Data linkage: Decisions around the analytic plan for this study are informed by the need for expediency to meet all deliverables in this rapid-turnaround, 2-year project. To ensure the primary analysis can be completed with up-to-date data covering the pandemic period, we must use the Medicare VRDC to access Medicare data. If the CRNs are able to provide high-quality Medicare identifiers for the included cohort (SSN, MBI, HIC, Name, DOB, Zip code, or other), it will be possible to link the measures of disease control derived from clinical laboratory testing data from the CRNs to the Medicare data set so that the secondary analysis can be completed with the same analytic files. To accomplish the data linkage each study site (WCM, UNC, MS, and UF) will submit a finder file with identifiers to HealthAPT (General Dynamics Information Technology), per CMS's 'Submission of Medicare Data Finder and Crosswalk Files' guidelines. In parallel, investigators from WCM will transmit the de-identified CRN data with clinical measures from Datacore to the VRDC, so that CMS can perform the crosswalk, merge the datasets, and discard the identifiers. The collaborating institutions and investigators will not have access to these identifiers in their analysis.

However, even if such identifiers can be provided by all CRNs, previous experience with this data suggests that up to 15% or more of each sample will fail to match either because of invalid identifiers or because of lack of overlap between the samples. This has the potential to introduce bias, as well as to decrease sample size. We will therefore conduct quality control on any provided identifiers before using them for the secondary analysis; large amounts of missingness or errors may mean that it will be more rigorous to conduct the secondary analysis separately on a CRN data set.

Data Management Plan

Data Collection: See section above for Data Collection description. Because of the need for expediency in this 2-year project, data queries for CRN and claims data will be conducted across distributed partners. HealthCore, a wholly-owned and independent outcome research subsidiary of Anthem, will be responsible for querying and analyzing Anthem data using the same methodology developed by the WCM team for analysis of the CRN and Medicare data. A similar distributed data model will be used by the Humana team for analysis of the Humana claims data.

Data Organization: All final analytic files for CRN and claims data analyses will be organized as patient-month records and generated and stored as comma-separated values files. We will collect PROs through survey data using RedCAP, a HIPAA-compliant IRB-approved platform. For the PRO analysis, analytic files will be organized as patient-encounter records and stored as comma-separated values files.

Data Handling: Medicare claims data will be accessed within the VRDC, and will be accessed and managed according to the Medicare specifications described in the DUA. Only 4 analysts will have access to VRDC. The VRDC will handle data backups. Commercial claims data will be handled within the commercial entity, with specified users described in the DUA.

CRN data and PRO data will both be handled within the Weill Cornell Data Core, a highly secure data repository and analytic environment maintained by Weill Cornell Information Technology Services. This restricted-access data center that meets the security requirements for PHI and other data designated as restricted access. Data Core's computing system belongs to a Windows domain that exceeds the U.S. Defense Department's C2 standards for trusted computing environments. Access is limited to authorized users who have signed a DUA with the Data Provider and a Computing System User Agreement with HPR Data Core, as confirmed by the WCM Office of Sponsored Research Administration and IRB. Data is backed up daily.

For all data sources, privacy and confidentiality will be maintained in accordance with IRB requirements. To limit risk, analyses will be performed on limited data sets, including no individually identifying information other than dates.

PRINCIPAL INVESTIGATOR: [name]; [name]

Data Description: We will utilize existing PCORnet CDM and Medicare LDS data dictionaries. A separate data dictionary will be developed for the PRO data. For in-house data sets, metadata will be documented within the Weill Cornell Data Catalog, which utilizes the elements from Dublin Core, with additional elements added from the following standards:

- Common metadata elements for Cataloging Biomedical Datasets
- DataCite Metadata
- Dryad Metadata
- W3C Data Catalog Vocabulary
- NIH BioCADDIE Metadata v1

This data catalog is maintained by the Weill Cornell's Samuel J. Wood Library and C.V. Starr Biomedical Information Center, which assists researchers in recording appropriate metadata needed for possible sharing and reuse of the data.

Data Maintenance: Raw data sources and analytic files used for this analysis will be maintained within the Data Core and/or within the secure computing environments of partner institutions that originally sourced the data for two years following conclusion of the project, at which point they will be destroyed.

Data Sharing: These analyses will use PHI, so the researchers will not share any data that is at the patient-level or patient-month level.

Data and Safety Monitoring Plan

A detailed Data and Safety Monitoring Plan (DSMP) will be submitted separately in an upcoming deliverable (12/21/20) in accordance with PCORI Policy on Data and Safety Monitoring Plans for PCORI-Funded Research.

Standards for Data Networks as Research Facilitating Structures

The study leverages the PCORnet National Patient-Centered Clinical Research Network (CRN) infrastructure through a collaboration among three CRNs to compare telemedicine's effectiveness on patient-centered outcomes, including the quality of health care and the frequency of avoidable emergency department visits and complications.

DN-1: Requirements for the design and features of data networks: The INSIGHT and OneFloridaCRNs require that affiliated sites structure their data according to the Observational Medical Outcomes Partnership (OMOP) data model, and transfer that data via Secure File Transfer to secure Data Centers managed by the CRN coordinating centers. Data from affiliated sites are transformed to fit the requirements of the PCORnet Common Data Model (CDM), which conducts nationally standardized data checks to ensure the validity and integrity of the data. The STAR CRN is a distributed network: each member institution maintains a local datamart meeting the PCORnet CDM specifications. While STAR does not house data within one central site, data may be transferred on a project by project basis via secure file transfer protocol or other secure mechanism acceptable to both parties. PCORnet utilizes the privacy-preserving record linkage solution provided by Datavant, providing software for each site that is installed locally to generate encrypted hash tokens based on personally-identifiable information held within local source systems, and then linking and standardizing patient data across health systems while protecting patient level identifiers.

PRINCIPAL INVESTIGATOR: [name]; [name]

The INSIGHT CRN leverages a rigorous set of privacy and security protocols that adhere to the HIPAA privacy rules and definitions of “Safe Harbor” and “Expert Determination” to undergird its limited, centralized database. A national expert has certified INSIGHT as meeting strong federal privacy and security requirements, and INSIGHT regularly undergoes audits to ensure compliance with NIST 800-66 and HIPAA standards. The INSIGHT CRN database is managed in the AWS cloud. OneFlorida makes use of a dedicated, secure ‘bubble’ for all project data. All access requires an encrypted connection over VPN and through the use of a VDI. STAR CRN institutions abide by local institutional security policies. At UNC-Chapel Hill (the STAR site participating in this project), data are housed as a HIPAA-limited dataset on a secure server and are only accessible to designated honest brokers. Each request for data requires an IRB approval or exemption designation; data request; review by a local data request review committee; and, if data is to be shared externally, a data use agreement. An honest broker extracts data on a project by project basis. Data are provisioned to local study teams on a secure file server restricted to the UNC VPN, or are securely transferred to approved, external parties.

INSIGHT, OneFlorida and STAR require researchers to follow policies and procedures for privacy and security. Researchers and project staff are trained regarding privacy and security, and data is only held on servers approved for holding PHI. Researchers and their institution are required to sign agreements which bind them to the CRN’s policies and procedures outlining requirements around data sharing, prohibiting re-identifying the data, requiring secure storage and disposal of the data, and requiring the reporting of breaches and security incidents. The CRNs maintain data dictionaries that are available to all researchers, which use a standardized terminology system to communicate the specific data elements and data structure contained in their respective databases. A PCORnet wide data dictionary annotating metadata within the CRNs is available to researchers as well. Consistent terminology used includes ICD-9 and ICD-10 codes for diagnoses, and LOINC codes for laboratory results among other commonly used coding terminologies in healthcare research. The Patient Centered Outcomes Research Network, of which the NYC INSIGHT network, OneFlorida and STAR are all members, is well-positioned to address our research questions through networks that have a proven track record of success in integrating large data sets from disparate institutions into a common data model suitable for developing and disseminating queries to be run at sites across the country.

DN-2: Selection and use of data networks: We have chosen to work with 3 established PCORI CRNs: INSIGHT, STAR, and One Florida. These networks represent very different patient populations, ranging from rural to urban, with great socioeconomic, racial, and ethnic diversity. Two of these networks (INSIGHT and One Florida in particular) have a track record of working together.

Very few networks have complete capture of the necessary variables and outcomes of interest within their Common Data Models for their patient populations. EHR data might be incomplete for several reasons: patients have ambulatory and inpatient encounters from health systems not affiliated with the CRNs, the post-acute care encounters (eg., hospice and home health) may not be covered by the EHR data. Since this project focuses on patient access to care and avoidance of unnecessary care and complications, it is of great importance to use data with complete patient utilization across multiple health systems, care settings, and geographic regions. We will therefore supplement the EHR data from CRNs with commercial and Medicare claims data. Claims data captures patient information as long as a patient is insured, regardless of the care settings and geographic regions. Using both EHR and insurance claims data therefore provided more complete and high-quality information for this project.

Statistical Methods

Causal Model and Overall Hypothesis

As described in more detail earlier, our population of interest is primary care patients with chronic medical conditions. The intervention of interest is the switch to primary care telemedicine prompted by the COVID epidemic. The

PRINCIPAL INVESTIGATOR: [name]; [name]

comparators are in-person care, telemedicine primary care, and telemedicine-supplemented in-person care; whether a practice is within any of these comparative groups may be time varying. The primary outcomes (described in more detail above) are unnecessary utilization outcomes listed above. The timing of the outcomes will be assessed at 30 days, 60 days, six months, and 12 months. The settings are primary care practices within our collaborating institutions.

